### Exclusion Criteria:

Second trimester (less than 28 weeks) BMI>50 Does not wish to participate

Patients in the 3rd trimester that require a digital cervical exam (DCE) for assessment of labor will be approached. After informed consent is obtained, one of two study investigators will perform a transperineal ultrasound (TPUS) using the glove-covered Butterfly iQ+ probe. The Butterfly iQ+ does not have a transperineal probe or setting, therefore, the "bladder" preset setting will be used. The "bladder" setting has been predetermined to provide the best cervical images. This pocket ultrasound is FDA-approved and is the standard of care for point of care ultrasounds in many institutions and is already used in our department. The TPUS will be performed by 1 of the 2 investigators with digital calipers. There will be 3 measurements: dilation, effacement, and station. The dilation measurements will be made from the inside margins of the cervix. Effacement will be measured by marking the thinnest and most easily imaged lip of the cervix. Zero station will be assumed to be 5 cm above the perineum, with distances from 6-10 cm corresponding to -1 to -5 station clinically. An independent, blinded examiner will then perform a traditional digital cervical exam, which will be recorded in EPIC. The study investigators will be blinded to the DCE measurement until the end of the study. The patient will act as their own control. Additionally, we will collect EGA, race, ethnicity, age, BMI, and indication for assessment of the

cervix. The patient will then be asked to score discomfort on a scale of 0-3 (none-extremely). They will then be asked to state if they preferred the TPUS, DCE or have no preference. At the end of the study the TPUS exams will be compared to the DCE, and a simple correlation will be calculated.

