## Protocol & Statistical Analysis Plan

Patients in the third trimester that present to the obstetrical triage for assessment of labor (contractions or rupture membranes) as well as patients admitted for labor and delivery will be approached. After informed consent is obtained, [name] or I will perform a transperineal ultrasound (TPUS) using the glove-covered Butterfly iQ+. An independent, blinded examiner will then perform a traditional digital cervical exam (DCE). The study PI's will be blinded to the DCE measurement until the end of the study. The patient will act as their own control. The patient will then be asked to score discomfort on a scale of 0-3 and preference for a method, if any. After 30 patients are enrolled, the PI's will compare the TPUS dilation measurements to the DCE dilation measurements and calculate a simple correlation. The discomfort scale will be analyzed using a Wilcoxon Signed Rank test.

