### **Data Analysis**

We chose a simple correlation  $r$  ( $r=0.5$ ). Using a two-tailed test, 5% significance level test ( $\alpha=0.05$ ) with power 80% power ( $\beta=0.2$ ), the required sample size is approximately ( $n=29$ ).

For the primary outcome, we will use the two-tailed test. For the secondary outcome (patient experience), we will use the Wilcoxon Signed Rank test.

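### If station is compared, a simple correlation of unclipped TPUS station with DCE station cannot reveal a zero-point error shared by all women, and no agreement statistic is planned

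*Combined protocol and SAP*

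**What the plan says.** The procedures text under Exclusion Criteria lists what the ultrasound yields: "There will be 3 measurements: dilation, effacement, and station". Station is not read directly but derived from a distance: "Zero station will be assumed to be 5 cm above the perineum, with distances from 6-10 cm corresponding to -1 to -5 station clinically". On the reference exam the text says: "An independent, blinded examiner will then perform a traditional digital cervical exam, which will be recorded in EPIC". It does not list which DCE components are recorded. The comparison is then given without naming a measurement: "At the end of the study the TPUS exams will be compared to the DCE, and a simple correlation will be calculated".

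The opening section, Protocol & Statistical Analysis Plan, is narrower. After 30 enrolments the investigators will "compare the TPUS dilation measurements to the DCE dilation measurements and calculate a simple correlation". Data Analysis sizes the study on a correlation of 0.5 and adds "For the primary outcome, we will use the two-tailed test", without saying which measurement is primary. No section plans another statistic comparing TPUS with DCE, such as a mean difference, limits of agreement, kappa or percent agreement.

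**The concern.** The mapping from distance to station rests on a zero point that the protocol itself calls assumed. Comparison with DCE station is the natural place for an error in that constant to show. A correlation cannot show it, because it does not change when the same amount is added to every value.

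If station is among the measurements compared, a high r could be taken to mean that TPUS station matches DCE station even when every TPUS value is off by a station or more. What is at stake is the interpretation of a station result. The dilation correlation and the sample size do not depend on the zero point.

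**Working it through.** **The plan's own figure.** Inputs from Data Analysis: r = 0.5, two-sided alpha 0.05, power 80%. The null value is not stated; r = 0 is assumed. By Fisher's z, n = ((1.960 + 0.842) / atanh(0.5))² + 3 = (2.802 / 0.5493)² + 3 = 29.01. The stated 29 reproduces. The zero point does not enter this calculation.

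**The algebra.** The protocol's mapping (5 cm is 0, and 6 to 10 cm are -1 to -5) is station = 5 - d, with d in cm. Let y be DCE station and c an error common to all women. Then corr(5 - d + c, y) = corr(5 - d, y) = -corr(d, y). The value of c drops out, and raw distance gives an r of the same size. The mean of TPUS minus DCE, in contrast, moves by exactly c. This step needs no assumed data.

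**A bare example (assumed data).** Take 30 women with DCE station spread evenly over -4 to 0, and TPUS equal to DCE apart from a common error. With a 1 cm error, r = 1.00 and exact agreement is 0%. With 2 cm, r is still 1.00 and exact agreement is still 0%.

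**A noisy example (all inputs assumed).** True station is N(-2, SD 1.5). TPUS is true station plus error N(0, SD 1). DCE is true station plus error N(0, SD 0.7), rounded to whole stations. There are 20,000 simulated trials of n = 30. Repeat runs differ by about 0.001 in r.

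| Condition | Mean r | Mean TPUS - DCE (stations) |
|---|---|---|
| Common offset 0 cm | 0.737 | 0.0 |
| Common offset 1 cm | 0.737 | 1.0 |
| Common offset 2 cm | 0.737 | 2.0 |
| DCE biased by -1 station, no offset | 0.737 | 1.0 |

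The last row shows that a mean difference does not identify its cause.

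**Where r does move (same inputs).**

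- Zero point varying between women with SD 0.5, 1 or 1.5 cm: mean r 0.709, 0.642, 0.564.
- TPUS station clipped to 0 to -5, with common offsets of 0, 1 and 2 cm: mean r 0.718, 0.691, 0.633.
- True scale of 0.8, 1.0 or 1.2 cm per station, with caliper error fixed in cm: mean r 0.679, 0.736, 0.774. The mean differences are +0.4, 0 and -0.4 station. If the measurement error scales with the distance instead, r stays at 0.737.

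**Precision of an agreement summary at n = 30.** The SD of the paired differences is not in the documents, so a range is assumed. The 95% CI half-width is t(0.975, 29) × SD / √30 for the mean difference and t(0.975, 29) × SD × √(1/30 + 1.96²/58) for each limit of agreement, with t = 2.045. For SD = 1.0 these are 2.045 / 5.477 = 0.37 and 2.045 × 0.3155 = 0.65.

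| SD of differences (stations) | Mean, ± | Each limit, ± | Power, true mean difference 1 station | Power, 0.5 station |
|---|---|---|---|---|
| 1.0 | 0.37 | 0.65 | >0.999 | 0.754 |
| 1.25 | 0.47 | 0.81 | 0.988 | 0.563 |
| 1.5 | 0.56 | 0.97 | 0.942 | 0.423 |
| 2.0 | 0.75 | 1.29 | 0.754 | 0.263 |

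**Values outside the mapped range.** In the noisy example with no offset, TPUS station has mean -2 and SD √(1.5² + 1²) = 1.80. About 13% of values lie above 0 (distance under 5 cm) and about 5% below -5 (distance over 10 cm).

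**The case against.** The strongest reply is that station may never be correlated. The only sentence that ties the correlation to a measurement names dilation, and the closing sentence of the procedures text may simply restate it. This stands, and it is why the point is conditional. The other reading remains open, because that closing sentence refers to the TPUS exams as a whole, after three measurements and an explicit conversion to clinical station.

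Second, no section claims that TPUS and DCE station are interchangeable, and nothing in the documents shows that the 5 cm value is wrong. Both are true. The concern is that the planned statistic could not tell either way.

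Third, a reader might infer that r is blind to every fault in the conversion. It is not: clipping, a zero point that differs between women, and a different true scale with caliper error fixed in cm can all change r. Only the unclipped linear conversion with a common shift leaves it exactly unchanged.

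Fourth, a reader might assume that paired station data are certain to exist. The text says only that the DCE is recorded in EPIC, and dilation is the only DCE component named anywhere. A recorded DCE station is plausible but inferred.

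Finally, correlation falls short of agreement for dilation too. That is fair as a general remark, but the assumed zero point enters only through station.

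**Conclusion.** The point holds as a minor, conditional one. If station is compared through 5 minus distance without clipping, r is identical for any zero-point error common to all women, and nothing else planned would show whether TPUS and DCE stations agree. The invariance is exact algebra. The simulated sizes (0.737 throughout, against mean differences of 0, 1 and 2 stations) rest on assumed spreads and errors.

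A reader might go further and conclude that the 5 cm assumption biases the planned correlation or undermines the study's size. The documents do not support that: a common shift cannot bias r, n = 29 reproduces, and on the dilation-only reading no planned result is touched.

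**What to change.** Reconcile the opening section, the procedures text and Data Analysis on which TPUS measurements are compared with DCE, and on which is primary.

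If station is one of them:

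- State the assumption that DCE station is recorded in EPIC on the same scale.
- Keep the correlation, and add the mean paired TPUS minus DCE station difference with its 95% CI and the 95% limits of agreement with their CIs.
- For this analysis only, compute TPUS station as 5 minus distance at every measured distance. Report how many distances fall below 5 cm and above 10 cm, since the protocol defines no station for either.
- Describe the result as a check of agreement, not as a test of the 5 cm assumption.

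The cost is one clarifying sentence and one short paired summary. If DCE station is recorded, no extra exam or patient is needed. The downsides are:

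- Precision at n = 30 is modest, as tabulated above, so a half-station difference may be missed.
- A difference may also come from DCE bias or from the scale.
- DCE station may be recorded in whole numbers, so the limits would be approximate.
- The line is extended past the protocol's stated range at both ends.

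### The only discomfort question follows both exams, so the ultrasound score needed for the signed-rank test would be recalled after the digital exam; state one score per exam and take the ultrasound score first

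*Combined protocol and SAP*

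**What the plan says.** The detailed procedures, printed under Exclusion Criteria, set out three steps in order.

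1. After consent, "one of two study investigators will perform a transperineal ultrasound (TPUS) using the glove-covered Butterfly iQ+ probe".
2. "An independent, blinded examiner will then perform a traditional digital cervical exam, which will be recorded in EPIC".
3. "The patient will then be asked to score discomfort on a scale of 0-3 (none-extremely". The preference question comes next: "They will then be asked to state if they preferred the TPUS, DCE or have no preference".

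The opening section, Protocol & Statistical Analysis Plan, gives the same order: "An independent, blinded examiner will then perform a traditional digital cervical exam (DCE") comes before "The patient will then be asked to score discomfort on a scale of 0-3 and preference for a method, if any".

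On analysis, the opening section says: "The discomfort scale will be analyzed using a Wilcoxon Signed Rank test". Data Analysis names the same test for patient experience, the secondary outcome. Both accounts of the procedures make each patient her own control. Neither places a rating between the two exams, says that two scores are taken, or gives the interval between the exams.

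**The concern.** A signed-rank comparison of the two methods uses the difference between a TPUS score and a DCE score in each patient. If both are collected after the DCE, the TPUS half of every pair is a recalled rating, made with the comparator fresh in mind. Recall or contrast could widen the difference or narrow it. On a four-level scale a one-point move is a third of the range.

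This is the named analysis of patient experience, and no later analysis can recover a TPUS score that was not taken before the DCE. The direct comparison is already collected by the preference question. The 0-3 scores therefore add most when they are separate ratings of each exam, and the present timing weakens that separation.

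**Working it through.** **1. The plan's own figure.** The only sample size stated is for the correlation: r = 0.5, two-sided α = 0.05, power 80%, n = 29 (Data Analysis). By Fisher's z:

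n = [(1.960 + 0.842) / atanh(0.5)]² + 3 = (2.802 / 0.5493)² + 3 ≈ 26.01 + 3 = 29.01.

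The figure is reproduced. It does not involve the discomfort score, for which no effect size or power is given.

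**2. What the test requires.** With T the TPUS score and D the DCE score, the test uses d = T − D per patient, drops zeros, ranks |d| as R, and takes Z = Σ R·sign(d) / √(Σ R²). Without both T and D there is no d. Two scores are thus implied. Since the only discomfort question comes after both exams, T is obtained after the DCE.

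**3. How much it could matter.** The documents supply only the planned enrolment of 30 and the 0-3 scale. The 5% two-sided level is borrowed from the primary test. Everything else is assumed:

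- Latent normal scores with within-patient correlation 0.6, cut into 0-3 at −0.5, 0.5, 1.3 (set A, mean DCE score 1.1) or at 0, 1.0, 1.8 (set B, generally low scores, mean 0.7).
- A share q of recalled TPUS scores moved by one point and kept within 0-3.

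Rejection rate with no true difference:

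| Error in the recalled TPUS score | q=0 | 10% | 20% | 30% | 40% |
|---|---|---|---|---|---|
| A, all one point lower | 5% | 7% | 12% | 21% | 33% |
| B, all one point lower | 5% | 6% | 9% | 16% | 24% |
| A, random direction | 5% | 5.1% | 5.0% | 5.2% | 5.3% |
| B, random direction | 5% | 5.0% | 5.8% | 6.6% | about 8% |

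Hand check of the mean shift. A score of 0 cannot fall, so one-way lowering shifts the mean by −q(1 − P₀), where P₀ is the share scoring 0.

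- A: P₀ = Φ(−0.5) = 0.309, so at q = 0.1 the shift is −0.1 × 0.691 = −0.07 points.
- B: P₀ = 0.5, so the shift is −0.05.

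Random errors shift the mean by (q/2)(P₀ − P₃), where P₃ is the share scoring 3. At q = 0.4:

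- A: 0.2 × (0.309 − 0.097) = +0.04.
- B: 0.2 × (0.500 − 0.036) = +0.09. This floor effect is why the rate in B drifts above 5%.

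The one-way result depends on the assumed correlation. In A at q = 40% it is 24% at correlation 0.3 and 45% at 0.8.

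Power when TPUS is truly less uncomfortable (A, correlation 0.6, q from 10% to 40%):

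| True effect | No error | Random direction | All one point higher | All one point lower |
|---|---|---|---|---|
| 0.5 SD | 68% | 59% to 36% | 42% to 5% | 77% to 94% |
| 1.0 SD | 99% | 99% to 88% | 95% to 39% | above 99% |

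**The case against.** **No bias is shown.** The documents give no interval between the exams, and recall may span only minutes. This stands: timing is established, distortion is not. A short interval limits forgetting, though not contrast with an exam just completed.

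**The large false-positive rates depend on one-way error.** This also stands. A reader might infer from the 33% figure that the plan favours TPUS or will probably produce a spurious finding. The documents support no direction and no share of patients. With errors in random direction the inflation largely disappears, leaving mainly a loss of power.

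**Scoring both exams together gives one frame of reference.** On a scale with little labelling this is a legitimate consideration, since scoring each exam at once lets a patient's use of the scale shift between ratings. Nor does the preference question measure the size of a difference. But preference already captures the side-by-side judgement, so the argument does not outweigh separate ratings.

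**Two scores are inferred.** True, and stating one score per exam is the more basic correction. A reader might go further and conclude that only one score is taken and the test cannot be run. The text does not say that, and the choice of a paired test points the other way.

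**The remedy is partial.** The DCE would still be rated second, and an investigator present at the first rating could influence it. Both points stand.

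**Conclusion.** The point holds as a cheap improvement to a secondary outcome. As written, the TPUS discomfort score would be given after the DCE. That rests on the sequence stated in two places and on the inference that a paired test needs one score per exam.

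Material bias is possible but not demonstrated. On the assumed inputs, the false-positive rate ranges from about 5% (random errors, up to about 8% with low scores) to 33% (40% of patients marking TPUS one point too low). Random errors cost power, for example from 68% to between 59% and 36% at a 0.5 SD effect. None of these is an estimate of what this trial will show.

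The primary correlation and n = 29 are unaffected.

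**What to change.** In the opening section and in the procedures under Exclusion Criteria, state:

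> The patient marks one 0-3 discomfort score for TPUS immediately after TPUS and before the DCE begins, and one 0-3 score for DCE immediately after the DCE. The Wilcoxon signed-rank test compares these two scores.

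Leave the preference question after both exams.

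The exam order need not change. With TPUS first, its measurements are complete before the study DCE result exists, which supports the stated blinding: "The study investigators will be blinded to the DCE measurement until the end of the study". Record as a limitation that the fixed order still confounds the discomfort comparison. The change removes recall and DCE contrast from the TPUS score only, and the DCE is still rated after TPUS.

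Cost: one extra tick-box, a brief pause before the DCE, and two or three sentences in the plan. No additional patients or staff are needed.

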### **Data Analysis**

We chose a simple correlation  $r$  ( $r=0.5$ ). Using a two-tailed test, 5% significance level test ( $\alpha=0.05$ ) with power 80% power ( $\beta=0.2$ ), the required sample size is approximately ( $n=29$ ).

For the primary outcome, we will use the two-tailed test. For the secondary outcome (patient experience), we will use the Wilcoxon Signed Rank test.

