### Inclusion Criteria:

Pregnant women in the third trimester presenting for assessment of labor or admitted for labor and delivery.

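### Does the plan need a rule for scans that give no ultrasound dilation, given that 29 counts complete pairs and analysis starts at 30 enrolled?

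*Combined protocol and SAP*

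**What the plan says.** The Data Analysis section sets the sample size for a correlation of 0.5 with 80% power: "Using a two-tailed test, 5% significance level test", and "the required sample size is approximately" 29. The opening section, Protocol & Statistical Analysis Plan, fixes when the comparison is made: "After 30 patients are enrolled". Each woman serves as her own control, so each contributes one TPUS dilation and one DCE dilation.

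The procedures text, which sits under Exclusion Criteria, describes the measurement. "The TPUS will be performed by 1 of the 2 investigators with digital calipers", and "The dilation measurements will be made from the inside margins of the cervix". The device "does not have a transperineal probe or setting", so the bladder preset is used; the same text says that this preset was chosen beforehand as giving the best images of the cervix. On blinding: "The study investigators will be blinded to the DCE measurement until the end of the study".

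Eligible women are those "presenting for assessment of labor or admitted for labor and delivery", with no upper limit on dilation. No exclusion concerns image quality. No section says what is done with a scan that yields no dilation, and none commits to reporting how many there were.

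**The concern.** A sample size for a correlation is a number of pairs, whereas the analysis is triggered by a number of women enrolled. Thirty enrolled against 29 needed leaves room for one lost pair (1/30 = 3.3%).

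The documents leave room for lost pairs. The probe is used without a dedicated setting, dilation needs two visible margins, and women in advanced labor can enter. If several scans failed, two things could be at stake:

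- **Power.** The correlation would rest on fewer pairs than planned.
- **Interpretation.** The correlation would describe only women who could be measured. A reader given r alone could not tell a method that always returns a value from one that fails in a fifth of women.

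A related worry is coding. If a fully dilated woman showed no margin and someone entered 10 cm after unblinding, r could rise.

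**Working it through.** **Inputs from the documents.** r = 0.5, two-sided alpha 0.05, power 80%, n = 29 (Data Analysis); comparison after 30 enrolled (Protocol & Statistical Analysis Plan). The number of failed scans is not given, so every loss count below is an assumption.

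**Step 1: reproduce the plan's figure.** By Fisher's z,

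n = ((1.960 + 0.842) / atanh(0.5))² + 3 = (2.802 / 0.549)² + 3 = 29.01.

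This gives 29 when rounded and 30 when rounded up. The stated 29 and the 30 enrolled agree with either.

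**Step 2: power if pairs are lost at random.** Power = Φ(0.549 × √(n − 3) − 1.960). The simulated column is the t-test of r in bivariate normal data.

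| Complete pairs | Lost of 30 | Fisher power | Simulated t-test power |
|---|---|---|---|
| 30 | 0 | 81.4% | 82.6% |
| 29 | 1 | 80.0% | 81.4% |
| 28 | 2 | 78.4% | 79.9% |
| 27 | 3 | 76.8% | 78.3% |
| 24 | 6 | 71.1% | 73.0% |

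By the t-test, two lost pairs still leave about 80%.

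**Step 3: power if the loss is concentrated at high dilation.** Simulate 30 women with r = 0.5 (bivariate normal), drop those with the highest DCE values, and test r in the rest.

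| Dropped | Median r | t-test power |
|---|---|---|
| 0 | 0.51 | 83% |
| 3 | 0.45 | 66% |
| 6 | 0.41 | 52% |

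This loss narrows the range of dilation, so both r and power fall. It makes a positive finding harder to reach, not easier.

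**Step 4: what a reader would see.** For an observed r = 0.5, the 95% interval is tanh(0.549 ± 1.960 / √(n − 3)): 0.17 to 0.73 with 30 pairs and 0.12 to 0.75 with 24. These intervals are hard to tell apart. The proportion measured differs clearly: 30/30 = 100% (Wilson 95% interval 88.6% to 100%) against 24/30 = 80% (62.7% to 90.5%). Giving the number of pairs next to r is enough to show this.

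**Step 5: the 10 cm entry.** Assume r = 0.5 in the other women, with a mean and SD of 3/1.5, 4/2 or 5/2.5 cm, and DCE = 10 in the fully dilated. Leaving one such woman blank gives a median r of about 0.51; entering 10 gives 0.73, 0.63 or 0.57. With three such women, the values are about 0.51 against 0.85, 0.75 or 0.66. The effect is large, but the plan defines dilation as a caliper distance between margins and nowhere provides for a substituted value. That no margin is visible at full dilation is also not stated in the documents.

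**The case for a change.** The strongest case for a change is that it is cheap and depends on timing. A few sentences and one field per scan would record why a scan gave no value, and that reason may not be recoverable later. How often a new method returns a reading is also central to comparing it with the standard exam. Blinding protects the measurement, but it does not settle a coding decision made after the DCE values are opened.

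Part of this stands. The plan does not say that 29 means complete pairs and does not promise a count. Recording the reason for each missing TPUS or DCE value would be good practice.

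The rest does not carry a change:

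- A correlation has no use for a woman with one reading, so complete pairs is the only natural analysis. Its n, set against 30 enrolled, already shows the shortfall.
- A proportion measured with its own interval would be a new outcome, and a correlation with 10 cm filled in would be a new analysis. Neither repairs anything stated.
- The power loss in Step 3 is not trivial, but a missing-scan rule would not recover it. Only more women would, and the documents give no failure rate from which to set their number.

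**Conclusion.** No change to the plan is needed. The figure of 29 is right, and 30 enrolled meets it with one pair to spare. The silence about failed scans is missing detail that an analyst fills in the obvious way: correlate the women who have both readings and state how many there were.

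With no failed scans nothing is affected. With 3 lost of 30, Fisher power is 77% if the loss is random; simulated t-test power is about 66% if the loss falls on the women with the highest DCE values. With 6 lost, the figures are 71% and about 52%. These rest on a true r of 0.5, bivariate normal readings and assumed loss counts.

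The conclusion also rests on the analyst following the caliper definition and entering no dilation where none was measured, which is how the procedures text reads.
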